4.3. Exclusion criteria

Participants will not be enrolled in this study if they meet any of the exclusion criteria:

13. Subjects actively or previously infected by SARS-CoV-2, as determined by a positive RT-PCR and positive serology test.
14. Subject currently working with high risk of exposure to SARS-CoV-2 (e.g. health care worker, emergency response personnel, etc....) or considered at the investigator's discretion to be at increased risk to acquire SARS-CoV-2 for any other reason.
15. Previous vaccination with an investigational COVID-19 vaccine.
16. History of or presence of pulmonary disorders (e.g. COPD, etc.) or asthma.
17. History or present of thrombocytopenia and/or bleeding disorders.
18. A positive serum pregnancy test at screening or urine pregnancy test prior to study injection, women who are planning to become pregnant during the study, or women who are breastfeeding.
19. Clinically relevant history of or current renal, hepatic, gastrointestinal, cardiovascular, respiratory, skin, hematological, endocrine, inflammatory, autoimmune, central nervous system or neurological diseases or clinically relevant abnormal laboratory values.
20. Use of immunosuppressive drugs like e.g. corticosteroids (excluding topical preparations and inhalers) within 3 months prior to the first vaccination or 6 months for chemotherapies and all along the study.
21. A diagnosis of schizophrenia, bipolar disease, or history of hospitalization for a psychiatric condition or previous suicide attempt.
22. A history of treatment for any other psychiatric disorder in the past 3 years that increases the risk to the subject in the opinion of the investigator.
23. Received immunoglobulin or other blood product within 3 months prior to enrollment or planned receipt of immunoglobulin or a blood product through study completion.
24. Vaccination within 4 weeks prior to first injection or planning to receive a licensed vaccine before D56 (e.g. *Inactivated influenza vaccine*).
25. Received measles-containing vaccine within 3 months prior to enrollment.

26. History of severe adverse reactions to vaccine administration, including anaphylaxis and related symptoms, such as urticaria, respiratory difficulty, angioedema and abdominal pain to vaccines, or history of known or suspected allergic reaction likely to be exacerbated by any component of the COVID-19 vaccine.
27. Participation in another investigational clinical study within four weeks before the screening visit or planned before the study completion.
28. Individuals who are living and/or working with severely immunocompromised people, pregnant women, lactating women, children under 12 months old, or any other individual that, in the judgment of the investigator, might be at increased risk.
29. Any condition that in the opinion of the investigator, may interfere with the aim of the study or the safety or wellbeing of the subject.
30. Subjects with any condition associated with, or that might be associated with, an increased risk of severe illness from COVID-19 according to US CDC definition³.
31. Subjects with confirmed or suspected immunodeficiency.
32. Exposure to an individual with confirmed COVID-19 or SARS-CoV-2 infection within the past 2 weeks prior to enrollment.
33. Subject with an acute disease and/or fever (body temperature > 38°C) at the time of the 1st vaccination visit.
34. History of confirmed SARS-CoV or MERS-CoV infection.
35. Current heavy smoker defined as smoking at least 20 cigarettes (1 pack, or equivalent) per day or former heavy smoker who was an active heavy smoker within the last year prior to the screening visit or has a total smoking history of ≥ 1 pack per day for 10 years or more.
36. Current or history of alcohol or drug abuse during the previous 3 years.
37. Presence of tattoos that, in the opinion of the investigator, would preclude evaluation of the injection site.

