| 
16.Exclusion criteria
 | 
 13. Subjects actively or previously infected by SARS-CoV-2, as determined by a positive RT-PCR and positive serology test. 14. Subject currently working with high risk of exposure to SARS-CoV-2 (e.g. health care worker, emergency response personnel, etc.) or considered at the investigator's discretion to be at increased risk to acquire SARS-CoV-2 for any other reason. 15. Previous vaccination with an investigational COVID-19 vaccine. 16. History of presence of pulmonary disorders (e.g. COPD, etc.) or asthma. 17. History or present of thrombocytopenia and/or bleeding disorders. 18. A positive serum pregnancy test at screening or urine pregnancy test prior to study injection, women who are planning to become pregnant during the study, or women who are breastfeeding. 19. Clinically relevant history of or current renal, hepatic, gastrointestinal, cardiovascular, respiratory, skin, hematological, endocrine, inflammatory, autoimmune, central nervous system or neurological diseases or clinically relevant abnormal laboratory values. |

20. Use of immunosuppressive drugs like e.g. corticosteroids (excluding topical preparations and inhalers) within 3 months prior to the first vaccination or 6 months for chemotherapies and all along the study.
21. A diagnosis of schizophrenia, bipolar disease, or history of hospitalization for a psychiatric condition or previous suicide attempt.
22. A history of treatment for any other psychiatric disorder in the past 3 years that increases the risk to the subject in the opinion of the investigator.
23. Received immunoglobulin or other blood product within 3 months prior to enrollment or planned receipt of immunoglobulin or a blood product through study completion.
24. Vaccination within 4 weeks prior to first injection or planning to receive a licensed vaccine before D56 (e.g. *Inactivated influenza vaccine*).
25. Received measles-containing vaccine within 3 months prior to enrollment.
26. History of severe adverse reactions to vaccine administration, including anaphylaxis and related symptoms, such as urticaria, respiratory difficulty, angioedema and abdominal pain to vaccines, or history of known or suspected allergic reaction likely to be exacerbated by any component of the COVID-19 vaccine.
27. Participation in another investigational clinical study within four weeks before the screening visit or planned before the study completion.

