| | 
11. Affilié(e) à un régime de sécurité sociale (sauf Aide médicale d'État) (uniquement pour la France).
 
12. Volontaire inscrit dans le registre informatisé du ministère français de la Santé et autorisé à participer à un essai clinique (uniquement pour la France).
 |
| 16. Critères de non-inclusion | 
13. Sujets précédemment ou actuellement infectés par le SARS-CoV-2, donné par un résultat virologique positif par RT-PCR et par un résultat sérologique positif.
 
14. Sujet ayant un travail présentant un risque élevé d'exposition au SARS-CoV-2 (ex. professionnel de santé, personnel d'intervention d'urgence, etc.) ou considéré, de l'avis de l'investigateur, comme présentant un risque élevé de contracter le SARS-CoV-2 pour toute autre raison.
 
15. Précédemment vacciné avec un vaccin expérimental contre la COVID-19.
 
16. Antécédents de maladies pulmonaires (ex. BPCO, etc.) ou d'asthme.
 
17. Présence ou antécédent d'une thrombocytopénie et/ou de troubles hémorragiques.
 
18. Test de grossesse sérique positif lors de la sélection ou test de grossesse urinaire positif avant l'injection du vaccin à l'étude, femmes qui prévoient une grossesse pendant l'étude, ou femmes qui allaitent.
 
19. Présence ou antécédents cliniquement significatifs de maladie rénale, hépatique, gastro-intestinale, cardiovasculaire, respiratoire, cutanée, hématologique, endocrinienne, inflammatoire, auto-immune, du système nerveux central ou neurologique, ou de résultats d'analyses biologiques anormaux et cliniquement significatifs.
 
20. Prise de médicaments immunosuppresseurs, ex. corticostéroïdes, (sauf les préparations topiques et les inhalateurs) dans les 3 mois précédant la première vaccination ou dans les 6 mois pour les chimiothérapies et tout au long de l'étude.
 
21. Diagnostic de schizophrénie, de bipolarité ou antécédents d'hospitalisation pour une maladie psychiatrique ou pour une tentative de suicide.
 
22. Antécédents de traitement pour tout autre trouble psychiatrique au cours des 3 dernières années qui, de l'avis de l'investigateur, peut induire un risque pour le sujet.
 
23. Utilisation ou utilisation prévue d'immunoglobuline ou autre produit sanguin dans les 3 mois précédant l'inclusion ou pendant toute la période de l'étude.
 
24. Vaccination avec un vaccin commercialisé dans les 4 semaines précédant la première injection ou prévue avant le J56 (ex. vaccin de la grippe).
 
25. Ayant été vacciné(e) avec un vaccin contenant la rougeole dans les 3 mois précédant l'inclusion.
 
26. Antécédents de réactions indésirables sévères suite à l'administration d'un vaccin, anaphylaxie et symptômes associés, tels qu'urticaire, difficulté respiratoire, œdème de Quincke et douleur abdominale liés à des vaccins, ou antécédents connus ou suspectés de réaction allergique susceptible d'être exacerbée par tout composant du vaccin contre la COVID-19.
 |

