4.8. Individual participants halting rules

The following are specific criteria for discontinuing individual participants from further vaccination, but not from completing scheduled follow-up assessments, unless the participant is explicitly withdrawn from the study:

- Participants who experienced a Serious Adverse Reaction (i.e. a Serious Adverse Event considered at least possibly related to vaccine).
- Participants who experienced a severe (grade 3 or higher) non-serious adverse event considered as at least possibly related to the vaccine
- Participants who develop a medical condition for which continued participation, in the opinion of the investigator, would pose a risk to the participant or would be likely to confound interpretation of the results
- Participants with a confirmed SARS CoV-2 infection given by a positive RT-PCR or a positive serology.
- Participants who donate whole blood or blood derivatives, tissue or organ all along the study.
- Participants who become pregnant during the treatment phase of the study.
- Participants not using a reliable method of contraception
- Participants who experience hypersensitivity reaction such as anaphylaxis within 24 hours or generalized urticaria within 72 hours after administration of the study vaccine
- Participants who use immunosuppressive drugs
- Participants who receive immunoglobulin or other blood product before study completion.
- Participants who live and/or work with severely immunocompromised people, pregnant women, lactating women, children under 12 months old, or any other individual that, in the judgment of the investigator, might be at increased risk from the first vaccination (D0) up to 28 days after the second vaccination (D56).

If any of these occur, appropriate measures to treat the participant will be taken and the participant will be asked to perform an ET visit if the participant is withdrawn (for any reason) from the study. The sponsor will be notified immediately.

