7.2. Study Visits

7.2.1. Screening visit (VS) (28 to 1 days before randomization)

After providing information on objectives, procedure and potential risk of the study, a sufficient time will be let to healthy volunteers (participant) for questions and answers and reflection as to whether or not he/she wishes to participate. Those willing to participate will be invited to sign an informed consent form and will be assessed for their eligibility to participate in the study. Screening tests will start only after the participant and Investigator have signed the informed consent form (ICF). Screening will take place from 28 days to 1 days prior to injection for the “Sentinel Groups” and to randomization/injection for the “Main Cohorts”.

The following screening assessments will be performed for each participant

- Participant identification
- Record of medical and surgery history (including history of measles infection)
- Record of prior and concomitant therapy (including history of measles immunization)
- Demographics: including Sex; month and year of birth; Height; Weight; BMI (calculated as Kg/m²)
- A complete physical examination
- Vital signs: blood pressure and heart rate (in sitting or supine position*), respiration rate (RR), body temperature,
- 12-lead ECG
- Laboratory safety screens as outlined in Appendix 1 (including blood pregnancy test for female subjects)
- Breath alcohol and urine drug tests (as outlined in Appendix 1)
- HBV; HCV and HIV serology**
- SARS-CoV-2 PCR and serology
- Compliance with inclusion/exclusion criteria

* Vital signs can be measured in sitting or supine position as well as long as within 1 patient the measurements are always done in the same position.

** Results of HBV, HCV and HIV serology will be communicated to participant unless he/she expresses the wish, via the Informed consent form, not to be informed.

At the end of the screening visit, the next visit (Visit 1) will be scheduled and confirmed (once results of laboratory safety test will be available and assess).

During the time window authorized for the screening visit, the Investigator may order a re-test of the following parameters: demographics (Height, weight and BMI), vital signs (HR, RR, BP, body temperature), 12-lead ECG, laboratory safety screen tests, breath alcohol and/or urine drug tests evaluated during the initial screening visit, if they need to evaluate the evolution of that parameter(s) or to confirm the value

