- An acute respiratory illness that is clinically consistent with COVID-19 based on presence of at least two of the following:
- Fever or history of new-onset fever (defined as body temperature of >38.0°C irrespective of method)

- New onset *lower* respiratory tract disease (LRTI) (any):
 - Persistent dry (non-productive) cough
 - Tachypnea or dyspnea
 - Low peripheral oxygen saturation (< 95%)
 - Radiographic findings consistent with LRTI
- New onset systemic symptoms consistent with viral illness (any):
 - Sore throat
 - Myalgia
 - Chills
 - Loss of smell or taste
 - Headache
 - fatigue
 - Congestion or runny nose
 - Nausea or vomiting
 - Diarrhea

AND

- Positive SARS-CoV-2 specific reverse transcriptase polymerase chain reaction (RT-PCR)

Severe COVID-19 clinical disease is defined as

- Virologically-confirmed COVID-19 clinical disease

AND

- A NEWS-2 score of >6

COVID-19-naive: Person testing negative for anti-SARS-CoV-2 antibodies at baseline [using an antibody test with high sensitivity]

Furthermore, the place of subject's residence, travel history and exposures to areas with known virus transmission within 15 days prior to the onset of symptoms have to be regarded when investigating a possible infection.

In case, the investigator cannot rule out a COVID-19 wild type infection, SARS CoV 2 PCR and serology will be performed.

If a subject is suspected/diagnosed with an actual COVID-19 infection he/she should not receive any subsequent study vaccination but should perform all visits for safety follow up reasons.

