12.1. Per-protocol and intention to treat analyses

The following populations will be defined and analyzed:

- In the Modified Intention To Treat (Modified ITT) population, all randomized/assigned subjects who received at least one injection are included in the analysis in the group in which they were initially randomized.
- The Per Protocol (PP) population is defined as all randomized/assigned subjects who received two injections according to protocol and completed the study without major protocol deviations. The PP analysis will be conducted based on the group in which the subjects were initially randomized/assigned.
- The modified ITT population will be used for the safety analyses, and will include sentinel subjects. The immunogenicity analyses will be performed in participants having received at least one injection (modified ITT population) as well as in participants having received two injections (PP population). For immunogenicity analyses, sentinel subjects will be included.

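### Exclusion criterion 13, read literally, excludes only volunteers positive on both RT-PCR and serology, which conflicts with section 4.8 and leaves recovered or early SARS-CoV-2 cases eligible

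*Protocol*

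**What the plan says.** Criterion 13 in Protocol section 4.3 names two states, active and previous infection, and defines them by one combined test result: "Subjects actively or previously infected by SARS-CoV-2, as determined by a positive RT-PCR and positive serology test". Item 16 of the English synopsis has the same condition, and the French synopsis uses the same conjunction: "donné par un résultat virologique positif par RT-PCR et par un résultat sérologique positif".

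Two other places in the protocol treat infection status differently:

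- Section 4.8, on stopping further vaccination of an individual: "Participants with a confirmed SARS CoV-2 infection given by a positive RT-PCR or a positive serology".
- Section 9.1.11, among the case definitions: "COVID-19-naive: Person testing negative for anti-SARS-CoV-2 antibodies at baseline". Neither the eligibility criteria nor the analysis populations use this term.

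The screening visit (section 7.2.1) includes "SARS-CoV-2 PCR and serology" for every volunteer, so both results are known before the first injection.

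Section 12.1 defines the modified ITT population so that "all randomized/assigned subjects who received at least one injection are included in the analysis in the group in which they were initially randomized". The per-protocol population is "all randomized/assigned subjects who received two injections according to protocol and completed the study without major protocol deviations". Immunogenicity is analysed in both. Section 12.4 places the analysis of variance of geometric mean titres (GMTs), across three vaccine groups and pooled placebo, in the per-protocol population. Under section 4.7, subjects who withdraw after randomisation are not replaced.

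**The concern.** The criterion is meant to keep out people who have or have had SARS-CoV-2 infection. A recovered person is typically PCR-negative and antibody-positive, and someone tested early in infection may be PCR-positive before antibodies appear. Each fails only one of the two tests, and the literal wording excludes neither.

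The secondary objectives concern spike-binding antibody, neutralising antibody and T-cell responses induced by the vaccine. A subject who already carries spike antibody blurs that measurement. In the placebo group such a subject raises the comparator titre. In a vaccine group, a recall response is counted with primary responses. Any seroconversion rule based on a rise from baseline is harder to interpret in either group. The groups are small (24 vaccinees per cohort, 18 placebo recipients in all), so one or two such subjects can matter. There is also a conduct problem: two sites in two countries have to interpret the same criterion, and the protocol gives them two different definitions of infection.

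**Working it through.** **Step 1: the criterion against section 4.8.** The protocol states no figure to reproduce here, because the issue is logical. There are four possible screening results:

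| RT-PCR | Serology | Likely state | Excluded by criterion 13 as worded? | Infection under section 4.8? |
|---|---|---|---|---|
| negative | negative | no evidence of infection | no | no |
| positive | negative | early active infection | no | yes |
| negative | positive | past infection | no | yes |
| positive | positive | later active infection | yes | yes |

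The literal wording removes one of the three infected patterns, while the section 4.8 definition covers all three. An antibody-positive volunteer is also not COVID-19-naive under section 9.1.11, yet may be enrolled.

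**Step 2: what happens to such a subject after enrolment.** The section 7.1 schedule checks individual halting rules only at contacts after the first injection, so the first injection is given whichever path follows.

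- *Section 4.8 applied:* no second injection. The subject cannot meet the two-injection condition of the per-protocol set, is not replaced, and stays in the modified ITT set.
- *Section 4.8 not applied:* the subject gets both injections. Having met the criteria as written, the subject is not an eligibility deviation and remains in both sets, so baseline spike antibody enters the GMT and seroconversion comparisons.

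**Step 3: illustrative size.** The protocol gives no seroprevalence, so 2%, 5% and 10% among those enrolled are assumptions. It is also assumed that every such volunteer who is otherwise eligible is enrolled. Group sizes are from Table 1 in section 3.3: total 30 + 30 + 30 = 90, placebo 6 + 6 + 6 = 18, vaccinees 24 per cohort.

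Expected number seropositive = 90 × p. Chance of at least one in a group of n = 1 − (1 − p)^n.

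| Assumed p | Expected of 90 | At least one of 18 placebo | At least one of 24 in a vaccine cohort |
|---|---|---|---|
| 0.02 | 1.8 | 1 − 0.98^18 = 0.305 | 0.384 |
| 0.05 | 4.5 | 1 − 0.95^18 = 0.603 | 0.708 |
| 0.10 | 9.0 | 1 − 0.90^18 = 0.850 | 0.920 |

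**Step 4: effect on a GMT, also conditional.** If k of n subjects have titres F times higher than they otherwise would, the group GMT is multiplied by F^(k/n). F is an assumption.

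- Placebo, n = 18, one subject: 10^(1/18) = 1.14 and 100^(1/18) = 1.29.
- Placebo, n = 18, two subjects: 10^(2/18) = 1.29 and 100^(2/18) = 1.67.
- Vaccine cohort, n = 24, one subject: 10^(1/24) = 1.10 and 100^(1/24) = 1.21.

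These multipliers apply to the modified ITT analysis on either path in step 2. They apply to the per-protocol GMT comparison only if section 4.8 is not enforced.

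**The case against.** The strongest reply is that the tests were meant distributively: RT-PCR for active infection, serology for previous infection. That is plausible. The criterion names two states and two tests, the strictly joint reading leaves almost nothing under previous infection, and both tests are run on everyone. A reader might go further and infer that the protocol deliberately admits recovered volunteers. The documents do not support that, since the stated target of the criterion says the opposite. What stands is that the operative wording does not say what was probably meant, in either language, while section 4.8 does use *or*.

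A reader might also infer that seropositive subjects necessarily bias the main GMT comparison. That does not follow either. If section 4.8 is applied, the subject misses the second injection and leaves the per-protocol set in which the analysis of variance is specified. What remains is a lost subject and an affected modified ITT analysis.

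Other criteria give partial protection. Criterion 14 excludes high-exposure workers, 32 recent contact with a confirmed case, 33 acute illness or fever at the first vaccination visit, and 29 anything the investigator thinks may interfere with the study's aim. Criterion 29 is discretionary. Criteria 32 and 33 miss asymptomatic cases without known contact, and section 1.1.1 puts asymptomatic cases at up to 40–50%. None of the four clearly catches a healthy recovered volunteer.

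Finally, the absence of an analysis set restricted to baseline-negative subjects might be read as a defect. It is not one on this document: such a subset, or a baseline adjustment, is commonly left to the SAP, and the protocol already plans N-antibody testing to separate infection from vaccine response. But an SAP cannot correct an eligibility criterion or undo an injection.

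**Conclusion.** The point holds as a wording error with practical consequences. Criterion 13 does not, as written, exclude the people it says it targets, and it disagrees with sections 4.8 and 9.1.11. It should be corrected whatever the authors intended, because the literal text governs eligibility at two sites.

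The size of the harm cannot be established from the protocol. At an assumed seroprevalence of 2% to 10%, 1.8 to 9 of 90 subjects and a 30% to 85% chance of at least one among 18 placebo recipients are illustrations of scale, not predictions. The GMT multipliers further assume a titre excess that the documents do not give. If sites apply the criterion distributively, the number enrolled with a detectable positive result falls to zero. The primary objective is safety. The effect on measurement falls on the secondary immunogenicity objectives, in a trial sized without a formal calculation and meant only to indicate big differences.

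**What to change.** In section 4.3 and in item 16 of both synopses, reword criterion 13 so that a positive RT-PCR *or* a positive serology at screening excludes the volunteer, which is what its stated target requires. In the same amendment, reconcile the criterion with section 4.8 and with the antibody-negative definition in section 9.1.11, so that one definition of infection runs through the protocol. This point takes no position on what the rule for stopping vaccination should be. How the analysis handles subjects whose day-0 sample proves N-antibody positive can be left to the SAP.

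The cost is a short amendment in three places and a few more screen failures. On the same assumed 2% to 10%, filling 90 places would need about 90 × 0.02 / 0.98 = 1.8 to 90 × 0.10 / 0.90 = 10 additional volunteers screened. No new test is needed.
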